CAT scan for extra-hepatic evaluation	X		X (in case of contraindication to MRI)	X	X (thoracic every 6 months)	X (thoracic)
Portal Doppler if thrombosis is suspected on imaging	X	X (recommended)				
ECG	X					
Evaluation of left FEV	X					
BIOLOGICAL ASSESSMENT						
Biological check-up	X*	X**			X (liver test)	X (liver test)
AFP marker	X				X	X
Serology (HBsAg, anti-HBs, anti-HCV)	X					
Pregnancy test (within 7 days of inclusion)	X					
BIOLOGICAL STUDY						
Samples: 2 EDTA tubes of blood then centrifugation for aliquoting of 4 cryotubes of plasma and freezing at -20°C then -80°C		X (D0, D1, D2 and D3 of 1 ^{ière} HEC)				
IMAGERY*** : CT cone beam or CT scan without injection during the procedure						

* Complete biological check-up: CBC/platelets, PT, AST, ALT, alkaline phosphatases, GGT, bilirubin (total, free and conjugated), factor V, blood ionogram, creatinine, albumin, blood sugar, blood calcium

** Biological check-up before each HEC: CBC, platelets, blood ionogram, creatinine, albumin, ASAT, ALAT, PAL, GGT, total and conjugated bilirubin, PT

*** : An anonymized copy of the imaging is to be sent to the FFCD for centralized review

**** : hepatic MRI (or CT) / ultrasound of the liver by a trained operator alternating every 3 months for 2 years

I. OBJECTIVES OF THE TRIAL

I.1 Main objective

The objective of this non-randomized phase II study is to evaluate the objective response rate (complete and partial response) at 6 months, assessed according to the mRECIST criteria in centralized review.

I.2 Secondary objectives

The secondary objectives of this study are to evaluate:

- The investigator-assessed 6-month objective response rate (mRECIST)
- Time to treatment failure
- The best answer according to mRECIST
- Objective response rate at 6 months (EASL)
- Progression-free survival
- Overall survival
- Tolerance of the treatment
- Quality of life (QLQ-C30 questionnaires and its HCC18 module specific to HCC)

II. PATIENT SELECTION

II.1 Inclusion criteria

- Histologically proven HCC or according to EASL/Barcelona criteria for nodules ≥ 1 cm
- Tumor not amenable to curative treatment (liver transplantation, surgical resection or percutaneous destruction)
- Measurable targets according to mRECIST v1.1 criteria
- Preserved liver function (in case of cirrhosis, Child-Pugh A or B7 without history of edemato-ascitic decompensation)
- Tumor classified as BCLC A or B without portal or extrahepatic invasion or C if WHO= 1

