- Digestive disorders: nausea, vomiting, diarrhea
- Stomatitis, esophagitis
- Elevated liver enzymes and bilirubin in 20-30% of cases
- Skin rash
- Acute heart rhythm disturbances, acute or late heart failure (rare before a cumulative dose of 93 mg/m²)
- Red coloration of the urine 24 to 48 hours after treatment.

As with other DNA altering anticancer agents, myelodysplastic syndromes and acute myeloid leukemias have been observed after combination therapy with anthracycline.

In case of idarubicin-related effects, no dose adjustment of idarubicin for loading the microbeads is planned. The chemoembolization session is then postponed or cancelled.

VII. MONITORING DURING AND AFTER TREATMENT

VII.1 Before each HEC

- Complete clinical examination: weight, vital signs, WHO general condition (which should be 0 or 1), pain assessment (VAS)
- Biological work-up: CBC/platelets, blood ionogram, creatinine, albumin, transaminases (AST, ALT), alkaline phosphatases (ALP), GGT, total and conjugated bilirubin, PT
- Adverse event evaluations of previous HECs according to NCI CTC version 4.0
- Quality of life questionnaires (QLQ-C30 and its module HCC18)

Prior to the session, the investigator should ensure that the patient has adequate hepatic and hematological function:

- Bilirubin ≤ 1.5 mg/dL, PNN $\geq 1,000/\text{mm}^3$, platelets $\geq 50,000/\text{mm}^3$, creatinine level $\leq 150 \mu\text{mol/L}$
- Hepatopoietic flow, thrombosis is considered significant if it involves at least 3 segments. The procedure is then contraindicated. A Doppler is strongly recommended before the embolization sessions to ensure that the procedure can be performed. It is recommended to evaluate these criteria according to the habits of the center.

For patients participating in the translational study: blood sampling for translational study (see paragraph IX)

VII.2 After each HEC

Hepatic MRI (or CT scan in case of contraindication to MRI) will be performed 4 to 6 weeks after each chemoembolization to assess their effectiveness.

Assessment imaging at 6 months from the date of inclusion MUST be performed regardless of the time of last HEC to assess the primary endpoint of the study.

Target measurements will be done according to mRECIST v1.1 to assess the primary endpoint of the study and according to EASL criteria to assess the secondary endpoint (Appendices 4 and 5).

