An anonymized copy on CD ROM (present in each observation book) of each morphological evaluation until progression (even if beyond 6 months) (MRI) is to be made. The copies will be sent to the CRGA of the FFCD for centralized review .

For the translational study, perform a cone beam CT acquisition or a hepatic CT scan without injection at the time of the 1^{ère} HEC.

For the clinical study, if possible, perform a cone beam CT acquisition at each HEC to assess the quality of the chemoembolization.

VII.3 Post-treatment monitoring beyond 6 months after inclusion:

After the end of chemoembolization treatment, patients will be followed according to TNCD recommendations:

Clinical and biological evaluation every 3 months for the first year and then every 6 months for 1 year:

- Clinical examination (weight, WHO)
- Biological tests: liver tests (ASAT, ALAT, GGT, bilirubinemia, albuminemia, TP)
- Marker : AFP

Morphological assessment:

- Chest CT scan without injection, every 6 months for 2 years
- Hepatic MRI (or CT scan) - liver ultrasound by a trained operator alternating every 3 months for 2 years

Monitoring data will be collected in the observation book during this 2-year period.

VIII. STOP PROCESSING THE STUDY

The processing of the study will be stopped in case of:

- Investigator's decision
- Major toxicity requiring discontinuation of treatment
- Serious or unexpected event requiring discontinuation of protocol treatment
- Progression of the disease
- Patient refusal or withdrawal of consent
- Death of the patient

In all cases of treatment discontinuation, the patient remains in the analysis for intention-to-treat and overall survival, and for 30 days after the last study treatment for toxicity.

There is no exclusion period for a subsequent therapeutic trial.

IX. TRANSLATIONAL STUDY

Only patients who have signed their translational-biological informed consent will be collected. Rationale for the study (see Appendix 15).

Blood sampling for VEGF determination

- 4 sampling times:

After the 1^{ière} HEC at D0, D1, D2 and D3

- Samples :

At each sampling time (4 times), collect 2 x 7 ml EDTA tubes of blood.

Centrifuge the blood tubes at room temperature at 1000 g for 15 minutes.

Collect the plasma to be distributed in a minimum of 4 cryotubes (minimum 1 mL per cryotube).

Identify the cryotubes with the patient's initials + inclusion number in the study, the sampling times.

Freeze the 2 plasma cryotubes at -20°C then at -80°C.

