Note: The time between collection and freezing (at -20°C) of plasma should not exceed 1 hour.

Complete the sample census form (present in the study investigator's binder) and send it by [contact]) or by email ([contact]) to the FFCD as soon as the 4 sampling times have been completed.

The repatriation of the samples to the CRB (biological resource center) EPIGENETEC of the FFCD, will be done at the end of the study by a specialized carrier.

Imaging for correlation with VEGF assay

Perform a cone beam CT or CT scan without injection after the 1^{ière} HEC.

An anonymized copy should be sent to the FFCD. A blank CD ROM is provided in the patient's CRF.

X. CENTRALIZED READING OF MRI AND CT

Responses will be evaluated according to the mRECIST version 1.1 (primary endpoint) and EASL (secondary endpoint) criteria (Appendices 4 and 5) and will be reviewed by a panel of independent radiologists who will confirm responses and dates of tumor progression or recurrence once all study examinations have been retrieved.

For this purpose, an **anonymized copy on CD ROM** (present in each observation book) **of each morphological evaluation until progression** (even if beyond 6 months) (MRI) is to be made. **The copies will be sent to the CRGA of the FFCD for centralized review.**

XI. MANAGEMENT OF SERIOUS ADVERSE EVENTS (SIA)

1. Security assessment parameters

Safety will be assessed by evaluating the general and clinical condition of patients and by collecting events occurring between visits during consultations. Toxicities will be assessed using the NCI-CTC-AE version 4.0 toxicity scale (see Appendix 6).

In case of an emergency, the patient, his family or his physician should call the investigator to warn of an event.

2. Definitions

a. Adverse Event (AE)

An adverse event is a harmful occurrence in a person who is a subject of biomedical research, whether or not the occurrence is related to the research or the product being investigated.

All adverse events will be recorded in the observation book on the pages provided.

b. Serious Adverse Event (SAE)

A serious adverse event (SAE) is considered to be any event:

- Resulting in death,
- Life-threatening,
- Leading to hospitalization or prolonged hospitalization,
- Causing permanent disability or severe temporary incapacity,
- Causing a birth defect, fetal malformation or abortion,
- Medically significant.

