- The rate of patients in objective response** (complete response or partial response) at 6 months according to mRECIST criteria and evaluated by the investigator.
- The rate of patients in objective response** (complete response or partial response) at 6 months according to EASL criteria assessed by the investigator and in centralized review.

- Time to treatment failure

It is defined as the time interval between the date of inclusion and the date of protocol treatment failure. Death, progression, and any discontinuation of protocol treatment (regardless of cause) are considered treatment failures.

Patients alive without failure will be censored at the date of the last 6-month morphological evaluation.

- The best response according to the mRECIST criteria

- Progression-free survival

It is defined as the time interval between the date of inclusion and the date of 1st progression according to mRECIST criteria (assessed in centralized review) or death (regardless of cause).

Patients living without progression will be censored at the date of last news.

- Overall survival

It is defined as the time interval between the date of inclusion and the date of death (regardless of cause) or the date of last news for living patients.

- Tolerance of the treatment

Toxicities will be evaluated by the NCI-CTC v4.0 criteria. They will be described according to their grade in terms of number of toxicities and number of patients who experienced the toxicity.

- Quality of life (QLQ-C30 questionnaires and its HCC18 module specific to HCC)

XII.3 Calculation of the number of subjects needed

The assumptions are:

- H0: A proportion of patients with an objective response at 6 months of 25% or less is not acceptable
- H1: A proportion of patients with an objective response at 6 months of more than 25% would demonstrate the effectiveness of the treatment. A rate of 40% is hoped for.

Using a 2-stage Fleming design (Fleming, 1982) with a one-sided alpha risk of 5% and power of 90%, it is necessary to include **86 treated and evaluable patients**.

At the 1^{ère} stage: 43 patients will be included

- If 10 or fewer patients have an objective response, the trial will be stopped for futility (H1 rejection)
- If 18 or more patients have an objective response, the trial will be stopped for efficacy (rejection of H0)

If not, we will go to 2^{ème} step including 43 additional patients

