### **7.4.2 Progression-free survival**

#### **7.4.2.1 Definition**

It is defined as the time between the date of inclusion and the date of first progression assessed by centralized review, or the date of death (whatever the cause). Patients alive without progression will be censored at the date of last evaluation.

Patients for whom no evaluation is available will be censored at inclusion date + 1 day.

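### Image copies for central review are required only until progression, in practice the site's own call, so centrally assessed PFS is open to an upward bias of unknown size

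*Protocol*

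**What the plan says.** Two rules govern which images reach the central panel.

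- Protocol VII.2 and section X: a copy "of each morphological evaluation until progression (even if beyond 6 months) (MRI) is to be made", and "The copies will be sent to the CRGA of the FFCD for centralized review". Neither section says whose progression is meant.
- Examination and follow-up schedule, footnote ***, attached to the morphological examinations: "An anonymized copy of the imaging is to be sent to the FFCD for centralized review". It sets no progression limit.

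Section X says the panel will "confirm responses and dates of tumor progression or recurrence once all study examinations have been retrieved". Protocol VII.2 also states: "Assessment imaging at 6 months from the date of inclusion MUST be performed regardless of the time of last HEC".

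PFS is a central endpoint in both documents. Protocol XII.2.2 counts "progression according to mRECIST criteria (assessed in centralized review) or death (regardless of cause"), and SAP 7.4.2.1 uses "the date of first progression assessed by centralized review" or death. The censoring rules differ. The protocol says: "Patients living without progression will be censored at the date of last news". The SAP censors at the last evaluation and does not say whether that means the last one read centrally. Neither document says what to do when the site calls progression and the panel does not.

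For the primary endpoint, SAP 7.3.1 uses the central read and falls back on the investigator's opinion when review is not possible.

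**The concern.** The event is decided by the panel, but the supply of images is cut off by someone else. Because central reading is retrospective, no central call exists when a site decides whether to copy a scan. Only the site's own judgement can stop the copies.

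If the panel agrees with the site, nothing is lost: the scan that showed progression should be in the file and PFS has its event. If the panel disagrees, the patient is event-free centrally and may have no later images, although the investigator believed the disease was growing. Such patients are likely to progress soon. Losing sight of them at that moment inflates PFS, and the SAP plans no analysis that would reveal it.

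A second consequence concerns the primary endpoint. A patient with local progression before month 6 must still have the 6-month scan, but VII.2 and X do not require its copy to be sent. That patient's result may then come from the investigator instead of the panel.

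**Working it through.** **1. Which call stops the copies.** VII.2 and X: copies until progression. X: panel reads after retrieval is complete. Together these leave only the local call. This is an inference from the two statements; no sentence says it. The phrase about going beyond 6 months extends copying for patients who have not progressed. It does not restore the 6-month copy for those who progressed earlier. The schedule footnote would restore it, so the passages conflict.

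**2. What happens to a patient whose local progression is not confirmed.**

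- SAP rule, read as the last centrally available evaluation: censored at the scan the site called progression. The censoring is informative.
- Protocol rule: censored at last news. Time with no central images counts as progression-free.
- Under either rule a later death still counts as an event, but late.

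Both rules move PFS upward.

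**3. Size, by assumption.** The documents give no PFS rate and no discordance rate. I simulated 400,000 patients with these assumptions: exponential time to progression, median 8 months; liver scans at 1.5, 3, 4.5, 6, 12, 18 and 24 months; follow-up uniform from 6 to 28 months; death after progression exponential, median 6 months; a share q of patients called by the site one scan before the panel would call them, with no later images.

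Check on the reference: 0.5^(12/8) = 35.4% at 12 months. The simulated Kaplan-Meier value with complete images is 34.7%; the small gap comes from the scan grid and from censoring at the last scan.

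| q | 12-month PFS, SAP rule | Excess over 34.7% |
|---|---|---|
| 10% | 36.7% | 2.0 points |
| 20% | 38.8% | 4.1 points |
| 30% | 40.9% | 6.2 points |

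- With scans every 3 months after month 6, the values are 37.3%, 39.4% and 41.6% against 35.1%: excess 2.2, 4.3 and 6.5 points.
- Under the protocol's last-news rule, they are 38.1%, 40.8% and 43.6% against 35.3%: excess 2.8, 5.5 and 8.3 points.
- If deaths are left out, the SAP rule gives 38.2%, 41.4% and 45.0% against 35.3%. That overstates the problem, because PFS counts death.
- If only half of the discordance is early local calls, the excess under the SAP rule falls to about 1-3 points.
- With q = 0 the excess is zero.

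For scale, the standard error of a 35% estimate in 44 patients, ignoring censoring, is √(0.35 × 0.65 / 44) = 7.2 points.

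**4. Design and primary endpoint.** The plan's figures reproduce. With 43 + 43 patients, stopping at ≤10 or ≥18 and a final cut-off of ≥29, the exact type I error at 25% is 0.047 and the exact power at 40% is 0.902. Allowing for 5% not evaluable, 86 / 0.95 = 90.5, hence 91. The image rule changes none of this.

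SAP 4.6.1 reports 22 responders among 44 evaluable patients against an adapted boundary of 19. The rate is 22/44 = 50%, with an exact one-sided 95% lower limit of 36.8%. Since 22 − 3 = 19, the efficacy conclusion survives the loss of three responders and fails at four. Under SAP 5.1.2 a patient with one chemoembolization and one post-treatment evaluation stays in the denominator. If an unsent 6-month scan was scored as non-response because the site had called progression, a central read could only keep 22 or raise it.

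**The case against.** The strongest reply has four parts.

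- **The footnote already asks for the copies.** A reader might infer from VII.2 and X that the 6-month scan of locally progressed patients is never read centrally. The documents do not support that. The footnote has no progression limit, and section X speaks of retrieving all study examinations. What stands is that sites have two conflicting instructions and the copy may not be sent.
- **The primary result is safe.** A reader might also infer that the fallback to the investigator inflates the response rate. An investigator who has called progression would most likely record non-response, which counts against the treatment. One caveat remains: V.2.3 allows a second session after a recurrence at 3 months, so an earlier call does not settle 6-month status. The direction is likely, not certain.
- **PFS is secondary and descriptive.** It is a Kaplan-Meier estimate in a single arm, with no test or decision rule, and the assumed bias is no larger than about one standard error. This stands and limits the importance. But a bias does not average out as sampling error does, and the confidence interval will not show it.
- **Discordance may run both ways.** This also stands. Where the site calls later than the panel, images keep coming and nothing is lost, so only the early-call share matters.

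**Conclusion.** The point holds in a limited form. The copy rules conflict, the stopping rule in VII.2 and X can in practice only follow the site's call, and no rule covers local progression that the panel does not confirm. Followed as written, those sections bias centrally assessed PFS upward under either censoring rule.

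The size cannot be derived from the documents. Under the assumptions above it is about 2-7 points at 12 months with the SAP rule read as the last centrally available evaluation, somewhat more with the protocol rule, less if discordance runs both ways, and nil under perfect agreement. Only discordant patients contribute.

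For the primary endpoint, the consequence is that some results may be local instead of central. The likely direction is conservative, and the documents give no ground for doubting the 22/44 result.

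**What to change.** 1. Reconcile the schedule footnote with Protocol VII.2 and X: copies of every scheduled liver MRI/CT, always including the 6-month scan, are sent through the 2-year follow-up whatever the local call. Making the end point centrally confirmed progression would not work, because the panel reads only after retrieval and sites would never learn of the confirmation.
2. State one PFS censoring rule, the last centrally read evaluation, in Protocol XII.2.2 and SAP 7.4.2.1.
3. In SAP 7.4.2, add one supportive PFS analysis that counts investigator-assessed progression as an event, with a table of local against central progression calls.
4. With the primary result, report how many patients were classified on the investigator's opinion.

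The cost is more image copies, some added reads by the existing panel, one further Kaplan-Meier analysis and one table. No new scans are needed and the sample size is unchanged. SAP 4.6.2 describes the final analysis as still to come, so the SAP additions remain possible, and missing copies of scans already performed can be requested from the sites.

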For evaluation of response to treatment (primary endpoint), perform MRI 4-6 months after each HEC. **Except in the case of bilobar disease (for which 2 sessions of HEC should be scheduled upfront), retreatment (new HEC treatment) will be performed according to follow-up MRIs.** An MRI will be performed 4 to 6 weeks after each chemoembolization treatment. In case of tumor remnant or recurrence treatable by HEC (i.e., no portal trunk thrombosis or in a territory ≥ 3 segments, hepatopoitic portal flow, WHO status < 2 , no hepatic decompensation, no extrahepatic metastasis), a new course of HEC should be performed targeting the remnant or recurrence (same distinction as above: supra-selective OR lobar approach). In the absence of tumor remnant or recurrence on MRI performed 4-6 weeks, MRI surveillance is performed every 3 months and the modalities of retreatment are the same as before.

In all cases, MRI at 6 months from the date of inclusion must be performed (primary endpoint of the study).

At the end of the session, embolization with additional material is not recommended.

If in case of a single HEC, a recurrence of the disease is observed at the 3-month MRI, a second HEC can be performed and will be performed as part of the protocol.

V.3 Premedication and concomitant treatments

Sufficient hydration (up to 2 liters per day), adapted to the cirrhotic context, will be prescribed before and after chemoembolization for at least 48 hours.

In case of nausea or vomiting, provide adequate treatment according to center procedures.

After the procedure, level 1 to 3 (WHO) analgesics will be used in an appropriate dose.

At the end of the procedure, the pain felt by the patient will be recorded using a visual analog scale (VAS rated from 0 to 10). If VAS > 3, titration of IV morphine by an IDE according to the recommendations.

Any treatment required for patient comfort will be prescribed at the discretion of the investigator. The use of a preventive anti-emetic treatment is recommended.

VI. EXPECTED TOXICITIES AND DOSE ADJUSTMENT

VI.1 Chemoembolization

The main adverse effects expected with chemoembolization are:

- Unwanted reflux or passage of microbeads into normal arteries adjacent to the targeted lesion or through the lesion to other arteries or arterial beds
- Non-targeted embolization
- Pulmonary embolization
- Ischemia in an undesired location
- Capillary bed saturation and tissue damage
- Rupture of a vessel or lesion and hemorrhage

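### After month 6 the centrally readable liver scan is scheduled only every 6 months, so later PFS progressions are dated late and an ultrasound can set the censoring date

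*Protocol*

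**What the plan says.** **Imaging after month 6.** Protocol VII.3 schedules liver MRI or CT, with "liver ultrasound by a trained operator alternating every 3 months for 2 years". The footnote to the examination schedule agrees: "hepatic MRI (or CT) / ultrasound of the liver by a trained operator alternating every 3 months for 2 years". One liver examination every 3 months, alternating between two types, puts MRI/CT at 6-month intervals. The other CT in this period is a chest scan without injection, also 6-monthly.

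**A different interval elsewhere.** Protocol V.2.3 says that if the MRI 4 to 6 weeks after a session shows no remnant or recurrence, "MRI surveillance is performed every 3 months and the modalities of retreatment are the same as before". It gives no end date.

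**PFS event.** Protocol XII.2.2 counts first "progression according to mRECIST criteria (assessed in centralized review) or death (regardless of cause"). The SAP (7.4.2.1 under Progression-free survival; the number is used twice) takes "the date of first progression assessed by centralized review, or the date of death (whatever the cause"). Protocol X, which describes that review, is headed for MRI and CT and has the panel confirm progression dates.

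**Censoring and analysis.** The SAP states: "Patients alive without progression will be censored at the date of last evaluation". It names no modality. Protocol XII.2.2 uses the date of last news instead, which SAP 6.2 sets by default to the last examination or monitoring performed. The analysis is Kaplan-Meier, with a median and rates at unspecified times and no interval-censored method.

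**The concern.** A progression can enter the PFS analysis only through an examination that the central panel can read. If that is MRI or CT, a liver progression arising after month 6 waits for the next such scan, up to 6 months away, and Kaplan-Meier treats the detection date as the event date. No text says how a progression suspected on ultrasound is dated, or that it triggers an MRI.

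The censoring rule adds a second route. A patient whose last examination was an unremarkable ultrasound can be counted progression-free to that date, although the last centrally readable scan was earlier.

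Both effects lengthen recorded progression-free time. The trial has a single arm, and protocol XIII says the data of the randomised trial of doxorubicin-loaded beads can be used for comparison on efficacy and safety. A PFS curve whose shape depends on scan spacing is a weak basis for such a comparison.

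**Working it through.** The documents give no expected PFS, event count or PFS power, so there is no figure of the plan to reproduce.

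**Inputs from the documents.** MRI/CT and ultrasound alternate every 3 months after month 6 (protocol VII.3 and schedule footnote). A mandatory scan falls at month 6 (V.2.3, VII.2). Before that, MRI is done 4 to 6 weeks after each session.

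**Assumptions, not in the documents.** PFS is exponential with true median m, so S(t) = 2^(-t/m) and λ = ln 2/m. Scans occur on schedule, at 1.5, 3, 4.5 and 6 months, then on one of three grids:
- 3-monthly MRI: 9, 12, 15, ...
- alternating, MRI first: 9, 15, 21, ...
- alternating, ultrasound first: 12, 18, 24, ...

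There is no unscheduled MRI. Deaths are ignored unless stated.

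**Direction.** Both alternating grids are subsets of the 3-monthly grid. Every recorded progression date is therefore the same or later.

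**Mean delay.** For a progression in a gap of length L, the mean wait is L/(1 - e^(-λL)) - 1/λ. With m = 8, λ = 0.0866 and 1/λ = 11.54:
- L = 3: 3/0.2289 - 11.54 = 1.56 months (3-monthly MRI).
- L = 6: 6/0.4054 - 11.54 = 3.26 months (ultrasound first).
- MRI first: one 3-month gap, then 6-month gaps: 0.2289 × 1.56 + 0.7711 × 3.26 = 2.87 months.

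For m from 5 to 15 months the ranges are 1.5-1.6 (3-monthly MRI), 2.8-2.9 (MRI first) and 3.1-3.4 (ultrasound first). If 20% of events are deaths (m from 6 to 15), they are 1.5-1.6, 2.7-2.9 and 3.1-3.2.

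**Rates, m = 8.** S(6) = 0.595, S(9) = 0.459, S(12) = 0.354.
- Ultrasound first: the curve at month 9 still stands at S(6), 60% against a true 46%. At month 12 it is correct.
- MRI first: the curve is correct at month 9. At month 12 it still stands at S(9), 46% against a true 35%.
- With 20% deaths, dated exactly, the recorded rate is 2^(-(0.8 × last scan + 0.2 × t)/m). This gives 56% at month 9 (ultrasound first) and 44% at month 12 (MRI first).

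**Medians, no deaths** (first scan with S(t) ≤ 0.5):

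| True median | 3-monthly MRI | MRI first | Ultrasound first |
|---|---|---|---|
| 5 | 6 | 6 | 6 |
| 7 | 9 | 9 | 12 |
| 8 | 9 | 9 | 12 |
| 10 | 12 | 15 | 12 |

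Alternation thus adds nothing or 3 months to the median, depending on m and the order.

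**Restricted mean to 24 months**, m from 6 to 15, deaths 0% or 20% of events: upward bias 0.7-1.1 months with 3-monthly MRI, 1.0-1.6 with MRI first and 1.2-1.9 with ultrasound first. The part due to alternation is about 0.3-0.8 months.

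These figures cover late dating only. The censoring effect depends on how many patients have an ultrasound as their last examination, which the documents do not give.

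**The case against.** - **The order is open.** Both passages name MRI first, but neither states a sequence. A reader who assumes ultrasound first might infer that all progressions between months 6 and 12 are dated at month 12, and that the median reads 12 instead of 9. The documents do not support this as a general statement: with MRI first, that contrast vanishes for true medians of 7 and 8 months. The distortion then moves to other times. This objection stands against any single headline figure, but not against the bias.
- **Not all of PFS is affected.** A reader might infer that PFS is readable only every 6 months and that all reported rates are inflated. Deaths are dated exactly, imaging before month 6 is denser, and a rate read at a scheduled MRI/CT time is correct under the assumptions. This stands.
- **Ultrasound or AFP may prompt an earlier MRI.** Suppose ultrasound detects 50-70% of progressions and an MRI follows. With m = 8 and ultrasound first, 0.2289/0.4054 = 56% of progressions in a gap arise before the ultrasound, and each one detected saves 3 months. The delay falls to 3.26 - 0.5 × 0.56 × 3 = 2.4, or 2.1 at 70%. It still exceeds 1.6.
- **Is ultrasound excluded from central review?** The mRECIST appendix is not in the text, so this rests on section X. The schedule lists ultrasound among the morphological examinations whose footnote asks for central copies. The ambiguity is real and needs resolving.
- **V.2.3 may cover only the treatment phase.** That is a possible reading, since VII.3 is headed for the period beyond 6 months. The missing end date leaves it unsettled.
- **PFS is secondary and descriptive**, and VII.3 says follow-up accords with national recommendations. Both points are correct. They limit the weight of the concern and explain why the remedy is analytical.

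**Conclusion.** The concern holds in a limited form. As written, the plan dates liver progressions after month 6 late and allows an ultrasound to set the PFS censoring date. Under exponential PFS with no unscheduled MRI, the mean delay exceeds that of 3-monthly MRI by roughly 1.1 to 1.9 months. The shift in the median ranges from none to about 3 months. Rates are overstated between MRI/CT dates and not at them.

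Three things are not established: the order of examinations, the true PFS, and whether the panel may read ultrasound. The imaging schedule of the outside trial is not in the documents either, so harm to that comparison is possible but not shown. The 6-month primary endpoint is untouched, because imaging at month 6 is mandatory.

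**What to change.** 1. In the PFS definition of SAP 7.4.2.1, define an evaluation as an MRI or CT readable by the central panel, so that an ultrasound never sets the censoring date. Align the last-news rule in protocol XII.2.2 with it.
2. Add a sensitivity analysis that treats progression as interval-censored between the last progression-free and the first progressive MRI/CT (for example, a Turnbull estimate). Report PFS rates at MRI/CT times.
3. Reconcile the 3-monthly MRI in V.2.3 with the alternation in VII.3, and state the order of examinations. Reconcile the schedule's request for central copies of morphological examinations with section X, which names only MRI and CT.

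The cost is SAP wording, a protocol clarification and one further analysis on dates already collected. SAP 4.6.1 reports that the trial stopped for efficacy after 46 inclusions, so the interval-censored estimate will be imprecise and belongs as a sensitivity analysis. The reported PFS may be less favourable.
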